6.1 Intent-to-Treat Population

Analyses will follow the intention-to-treat (ITT) principle in which subjects will be analyzed in the condition to which they were randomized, regardless of whether they received the assigned intervention. Primary analyses will be based on the ITT population, which includes all randomized subjects.

6.2 Per Protocol and Complier Population

A secondary analysis of the primary outcome will be completed for the per-protocol population, defined as a subset of the ITT population who completed the 2-3 months intervention period, had no hearing aid intervention drop-in for the control condition, and had no major protocol deviations. Major protocol deviations include violations in inclusion and exclusion criteria at enrollment and poor compliance with hearing aids for the hearing aid intervention condition, defined as subjects who discontinue hearing aid use. All major protocol deviations will be identified in a blinded fashion prior to database lock. Complier average causal effect analysis will also be conducted to mitigate bias present⁵ in per protocol analyses.

7. Statistical Analysis

7.1 General Considerations

Study data will be monitored on an on-going basis by the ACHIEVE Data Coordinating Center (DCC). The DCC will send data clarification requests to the clinical sites for resolution while the study is on-going. Final cleaning and editing of the study database will be carried out after the final participant completes their last follow-up visit. Unblinding of treatment assignments will not be performed until the study data are cleaned, queries resolved, and database lock achieved. A permanent archive of the database will be maintained by the DCC. Randomization, stratified by ARIC study status, center, and hearing impairment level is completed within CDART, the DCC's data management system. Built-in algorithms first check for missing key items and eligibility criteria, reducing protocol violations associated with enrollment. Although the ACHIEVE hearing aid intervention is, by nature, un-masked, to minimize bias based on review of accumulating data by the project team, the ACHIEVE PI, co-investigators, and key project staff, except for key data coordinating center staff, will remain blinded to accumulating data. This will be done by applying a dummy ID onto the treatment-specific data forms as they are transferred from CDART to SAS for data cleaning and interim reporting.

This statistical analysis plan (SAP) was developed prior to review of the study dataset and under the assumption that all data were collected in adherence to the protocol and in accordance with good clinical research practices. As the data are analyzed, some deviation is anticipated (e.g., missing data; small sample sizes). In instances where these deviations would make the proposed analyses inappropriate, modifications to the analysis plan will be made and noted in the final report.

Consistent with best practices in clinical trials, we will assess the comparability of the randomized conditions with respect to known baseline confounders, such as hearing loss (pure tone average in the better hearing ear <40 db vs 40+ db), recruitment source (ARIC vs de novo), center, age, sex, education, and the presence of APOE ε 4 alleles⁶. If, despite randomization, there is an imbalance between the treatment conditions we will adjust for relevant confounders as well as explore the use of a precise, locally efficient, augmented, simple estimator⁷ which may offer greater precision.

At the outset of the study, an in-clinic neurocognitive assessment comprised of ten tests (see table 7.1) was administered. The assessment included the delayed word recall (exposure and recall)⁸ logical memory test (I and II)⁹, incidental learning test¹⁰, word fluency test (letters F, A, and S)¹¹, animal naming test¹¹, Boston naming test¹², digit symbol substitution⁹, trail making tests parts A and B¹³, and the digit span backwards⁹. All ten tests were used to compute a global cognitive function factor score (described in section 8.0) for each participant¹⁴ that was standardized to the baseline of the study.

Due to the outbreak of COVID-19 (see section 9.0 for details), a modified six-test phone-based neurocognitive assessment was administered beginning in July 2020. The assessment included the Consortium to Establish a Registry for Alzheimer's Disease (CERAD) word list (immediate and delayed)¹⁵

an abbreviated version of the word fluency test (letters F and A), the animal naming test, oral versions of trail making tests parts A and B, and the digit span backwards. The six tests were utilized to compute a phone-based global cognitive function factor score.

In-person administration of the original ten tests resumed in June 2021. All ACHIEVE participants will be invited to complete an in-person assessment even if the target date for the 36-month follow-up has passed. If a participant does not complete an in-person assessment, an in-person global cognitive function factor score will be imputed (see section 7.3).

ACHIEVE in-clinic test order ¹	ACHIEVE telephone test order ¹
Ensuring Speech Understanding	Ensuring Speech Understanding for Telephone
Mini Mental State Exam (MMSE)	MMSE / CDR - Participant Hybrid for Telephone ²
Delayed Word Recall - Exposure	CERAD Immediate ³
Digit Symbol Substitution	Digit Span Backward
Delayed Word Recall	CERAD Delayed ³
Incidental Learning	Oral Trails A ²
Word Fluency (FAS)	Oral Trails B ²
Animal Naming	Word Fluency (FA)
Logical Memory I	Animal Naming
Digit Span Backwards	
Trails A	
Trails B	
Boston Naming	
Logical Memory II	

 Table 7.1. ACHIEVE Neurocognitive Test Battery Components

¹Test order changes across modes of administration to enable timing delays for memory tests.

²Modification applied to the in-clinic version of the neurocognitive test for telephone administration.

³Indicates neurocognitive test not included in the original 10-test battery.

All programs used in the statistical analysis of study data will be documented, tested, and archived. Archiving of statistical analyses at the DCC includes the original written specifications for the analyses, any subsequent modifications, the computer program file, and the log, list and other output files produced by the program. The DCC will undertake all the analyses of study data using SAS® version 9 or later. The factor analysis will be performed using Mplus 8.6 or later.

7.2 Primary Outcome

The primary outcome is cognitive decline, as measured by the change in a global cognitive function factor score. The factor score is derived from a confirmatory factor analysis model that identifies common covariation among all cognitive tests administered in-person. Factor scores are generated for each participant at each in-person assessment using a measure harmonization and item banking approach^{16, 17}. Factor loadings and latent means for each neurocognitive test are estimated using data from the ACHIEVE baseline. The mean of the global cognitive function factor score at the baseline is set to 0 and the SD is set to 1. Fixed parameter estimates from the baseline model are then integrated into models that estimate the factor mean and SD at each subsequent assessment. This process ensures that changes over time represent changes in the underlying factor rather than changes in the scaling or meaning of the constructs. The assumption of longitudinal measurement invariance is supported by prior studies that utilized similar neurocognitive tests^{18, 19}. A final fixed parameter model analyzes available data collected in-person and

computes a global cognitive function factor score for each participant at every assessment in which one or more neurocognitive tests were completed. A comparable process is used to generate factor scores for the cognitive domains of memory, executive functioning, and language.

7.3 **Primary Analysis**

We will examine cognitive decline within each condition using mixed effects models that account for the correlation among repeated measures as well as the correlation between spouses or cohabitating partners. If a linear trend appears reasonable, we will fit a model with a linear slope. If a nonlinear trend is observed, the model will be adapted to include time splines²⁰. Continuous time in years from the baseline will be the time scale. An interaction term between treatment assignment and time will be used to test if rates of cognitive change differ by treatment assignment. Model fit will be assessed with residual plots and other statistics (Akaike Information Criterion, Bayesian Information Criterion, etc.). The primary analysis may include adjustments for the baseline hearing loss, ARIC vs de novo status, center, age, sex, education, and APOE ϵ 4 alleles.

Missing cognitive factor scores among ACHIEVE participants will be generated utilizing multiple imputation by chained equations²¹. The number of imputations needed to generate valid parameter estimates will be determined by a two-stage analysis²². The imputation model will include (1) in-person cognitive factor scores, (2) MMSE and Six-item Screener scores, (3) adjudicated incident MCI or dementia, (4) race, (5) time variables indicating when a participant with missing data might have completed an assessment based on time from randomization to missed visit, and (6) all previously listed covariates. Interactions between variables in the imputation model will be tested and added as necessary. The imputation will be conducted in stages so that concurrent and past measurements, but not future measurements, inform the imputed values. The validity of the imputation model will be assessed by comparing observed values to imputed values among a 20% sample selected at random and a 20% sample selected based on the probability of missingness estimated from a logistic regression model.

The primary analysis will focus on cognitive factor scores imputed prior to death. An analysis comparing pre- and post-death cognitive factor scores will be performed using values generated from an imputation model in which death is included as an auxiliary variable. A similar procedure will be used to contrast pre- and post-dementia cognitive factor scores.

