### **Primary Analysis**

Groups will be compared for the primary outcome using mixed effects models that account for the correlation among repeated measures as well as the correlation between spouses or cohabitating partners. If a linear trend appears reasonable, we will fit a model with a linear slope. If a nonlinear trend is observed, the model will be adapted to include time splines. Continuous time in years from the baseline will be the time scale. An interaction term between treatment assignment and time will be used to test if rates of cognitive change differ by treatment assignment. Model fit will be assessed with residual plots and other statistics (Akaike Information Criterion, Bayesian Information Criterion, etc.). The primary analysis may include adjustments for the baseline hearing loss, ARIC vs de novo status, field center, age, sex, education, and APOE ε4 alleles.

Missing cognitive factor scores among ACHIEVE participants will be generated utilizing multiple imputation by chained equations. The number of imputations needed to generate valid parameter estimates will be determined by a two-stage analysis. The imputation model will include (1) in-person cognitive factor scores, (2) MMSE and Six-item Screener scores, (3) adjudicated incident MCI or dementia, (4) race, (5) time variables indicating when a participant with missing data might have completed an assessment based on time from randomization to missed visit, and (6) all previously listed covariates. Interactions between variables in the imputation model will be tested and added as necessary. The imputation will be conducted in stages so that concurrent and past measurements, but not future measurements, inform the imputed values. The validity of the imputation model will be assessed by comparing observed values to imputed values among a 20% sample selected at random and a 20% sample selected based on the probability of missingness estimated from a logistic regression model.

The primary analysis will focus on cognitive factor scores imputed prior to death. An analysis comparing pre- and post-death cognitive factor scores will be performed using values generated from an imputation model in which death is included as an auxiliary variable. A similar procedure will be used to contrast pre- and post-dementia cognitive factor scores.

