Changes from version 3.0 to 4.0

Affected section	Brief description of change	Brief rationale for change
7.1, General	Added threshold for dichotomization of	Clarified how hearing loss would be
Considerations and	hearing loss and removed the ambiguous	defined as a covariate in the primary
7.3 Primary	term "stratum".	analysis.
Analysis		
7.1 General	Removed phone-based cognitive scores	A test of 35 separate models revealed that
Considerations	and added race to the imputation model.	phone-based global cognitive function
7.3 Primary	Removed the sentence "The phone-based	factor scores did not improve the
Analysis	global cognitive function factor score	performance of the imputation model.
	will be included in the imputation model	However, adding race as an auxiliary
	as an auxiliary variable."	variable resulted in a small improvement.

7.3 Primary	For the primary analysis the time scale	Clarified the timeframe for cognitive
Analysis	was specified as "years from the	decline.
	baseline."	

Changes from version 4.0 to 5.0

Affected section	Brief description of change	Brief rationale for change
7.5 Secondary	Clarified that results from the analysis of	Specified the importance of examining
Outcomes	secondary outcomes will be included in	intervention effects on both cognitive
	the primary outcome manuscript	decline and adjudicated dementia.

Changes from version 5.0 to 5.1

Affected section	Brief description of change	Brief rationale for change
7.5 Secondary	Clarified definition of secondary outcome	Specified source of information for
Outcomes	and described sensitivity analyses.	adjudicated MCI and dementia.

Changes from version 5.1 to 5.2

Affected section	Brief description of change	Brief rationale for change
7.7 Adjustment for	Clarified use of Hochberg modification	Specified that the Hochberg modification
Multiple	to the Bonferroni adjustment.	to the Bonferroni adjustment will be
Comparisons		applied to five outcomes (1) decline in
		global cognitive function, (2) time to
		incident cognitive impairment, (3)
		decline in memory domain, (4), decline
		in executive function domain, and (5)
		decline in language domain.

SAP Signatures

DSMB Board and National Institute on Aging	June 2, 2022
Principal Investigator – [name], PhD	May 16, 2022
Protocol Statistician – [name]	May 16, 2022

TABLE OF CONTENTS

1.	Int	roduction	7
2.	Ba	ckground	7
3.	Ob	jectives	7
4.	Stu	ıdy Design	7
4.	.1	Inclusion Criteria	8
4.	.2	Exclusion Criteria	9
5.	Pov	wer	9

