7.4 Sensitivity Analyses of the Primary Outcome

Additional analyses of the primary outcome may include, but are not limited to:

- (a) An analysis of global cognitive function in which data from in-person cognitive evaluations will be stratified by condition before a factor score is computed for each participant. The factor scores generated will be standardized using the condition-specific baseline mean and SD.
- (b) An analysis of a co-calibrated^{23,24} global cognitive function factor score in which the ten tests administered in-person and the six tests administered over the phone will be included in the confirmatory factor analysis model. Modeling constraints will be applied to scale the co-calibrated factor score to the same metric as the in-person factor score utilized in the primary analysis²⁵. Mode of data collection (in-person, phone) will be included in the analytic model as a covariate.
- (c) Use of full-information maximum likelihood to account for missing data. Parameter estimates from these analyses will be compared to estimates from multiple imputation analyses to gauge the impact of including auxiliary variables in the imputation model.
- (d) Control-based multiple imputation, in which missing values of the primary outcome for the hearing aid condition without a dementia diagnosis are imputed based on the successful aging control intervention condition. This analysis will investigate the strength of the primary analysis results to the missing at random assumption.

- (e) Analysis of cognitive decline based on a categorized version of time (visits) rather than continuous time in years.
- (f) A replication of the primary analyses stratified by subgroups of ARIC vs de novo participants. Interaction between intervention condition and recruitment group will be tested in additional models relative to p < 0.10.
- (g) Exploration of the impact on the primary analysis by further adjustment for additional explanatory variables, as mentioned in section 7.1.

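### The imputation model for the primary outcome does not list randomised arm; followed as written, it biases the treatment-by-time estimate toward zero, by an amount the documents do not settle

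*SAP*

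**What the plan says.** The primary test is a mixed-model interaction (SAP 7.3): "An interaction term between treatment assignment and time will be used to test if rates of cognitive change differ by treatment assignment". Missing factor scores are filled by chained equations. The inputs are enumerated: "The imputation model will include (1) in-person cognitive factor scores, (2) MMSE and Six-item Screener scores, (3) adjudicated incident MCI or dementia, (4) race", then (5) variables for when a missed assessment would have taken place, "and (6) all previously listed covariates". Protocol 12.2, under Primary Analysis, has the same list, beginning "The imputation model will include (1) in-person cognitive factor scores, (2) MMSE and Six-item Screener scores".

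Item (6) points back to the adjustment covariates: hearing loss, ARIC status, center, age, sex, education and APOE ε4. Treatment assignment is named just before them, but only as part of the analysis model.

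Three further statements bear on the point:
- SAP 7.3 on interactions: "Interactions between variables in the imputation model will be tested and added as necessary". This covers variables already in the model.
- SAP 7.3 on staging: only past and concurrent measurements may inform an imputed value.
- SAP 7.3 on deaths: "The primary analysis will focus on cognitive factor scores imputed prior to death".

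The SAP change log for version 4.0 shows the inputs being edited one at a time: phone-based scores were removed "and added race to the imputation model".

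**The concern.** A score imputed from a model that ignores arm is drawn around a trajectory pooled over the two arms. Each such score adds little or nothing to the between-arm difference in slope, so a real difference shrinks in proportion to how much of the slope information is imputed.

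Two features of the plan limit self-correction. Because future values may not inform past ones, an observed Year 3 score cannot carry arm information back to a missed Year 1 or 2 score. The planned validation compares observed with imputed values in two 20% samples and states no comparison by arm, so a pooled model could pass it.

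What is at stake is the size of the reported effect. The memory, executive function and language scores use the same methods (SAP 7.5), so four of the five outcomes in the multiplicity set are affected. The comparison of full-information maximum likelihood with multiple imputation in SAP 7.4(c) is meant "to gauge the impact of including auxiliary variables in the imputation model"; a gap caused by the missing arm term would be credited to the auxiliary variables.

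**Working it through.** **1. Inputs.** Control slope -0.08/year and hearing-intervention slope -0.052/year, a difference of 0.028/year; 0.08 - 0.057 = 0.023/year after drop-in/drop-out (SAP 5.1). SD of 3-year change 0.27 (Protocol 12.1). N = 977 (SAP 5.2). Attrition 6.7% at October 2021, in a paragraph that counts withdrawal and mortality (SAP 5.1). Enrolment November 2017 (SAP 4) to 25 October 2019 (SAP 9). In-person testing stopped in March 2020 (SAP 9) or mid-2020 (SAP 4), and resumed in June 2021 (SAP 7.1).

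**2. The plan's own figure.** For 850 randomised, n per arm = 425 × 0.9³ = 309.8 and the diluted 3-year difference = 0.084 × 0.85 = 0.0714. SE = 0.27 × √(2/309.8) = 0.0217. Power = Φ(0.0714/0.0217 - 1.96) = 0.91, against the stated 90% (Protocol 12.1). With the rounded difference 3 × 0.023 = 0.069, it is 0.89. The inputs are therefore read as the plan uses them.

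**3. Share of scores missed through closure.** With uniform enrolment over about 23.8 months and a mid-March 2020 start, Year 1 visits falling in the closure are about 7.3/23.8 = 31% and Year 2 visits about 15/23.8 = 63%. With a 1 July 2020 start they are about 3.8/23.8 = 16% and 11.5/23.8 = 48%. Allowing the enrolment shapes compatible with about 200 participants having 1-year data in June 2019 (SAP 5.2) gives 29-39% and 62-66% (March), or 15-21% and 47-54% (mid-2020).

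**4. Hand check of the attrition-only ceiling.** If all 6.7% were lost before Year 1 and imputed without arm, their expected between-arm difference is zero. The estimate is then (1 - 0.067) × δ = 0.933δ, a shrinkage of 6.7%.

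**5. Simulation.** Random intercept and slope plus residual, with slope variance = (0.27² - 2 × residual variance)/9. The residual SD per visit is not given; 0.05 to 0.15 was tried. Sequential regression imputation used past and concurrent data only, without and with arm. Dropout was independent of arm, and spouse pairs were not modelled. Shrinkage of treatment by time with arm omitted:

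| Setting | Shrinkage |
|---|---|
| A. 6.7% attrition, all imputed, spread over Years 1-3 | 3.2-5.2% |
| A, all losses at Year 3 | 0.6-3.2% |
| A, all losses before Year 1 | 6.6-6.8% |
| A, half the losses deaths (assumed), not imputed | 1.6-2.7% |
| B. Closure-missed Year 1/2 scores left missing, only Year 3 imputed | 4.3-6.2% |
| C. Closure-missed Year 1/2 scores also imputed: March start; mid-2020 start | 10.2-14.1%; 7.1-12.4% |
| C, half the losses deaths | 8.7-11.7%; 5.5-10.0% |
| C, all losses at Year 3 | 9.4-13.1%; 5.5-10.6% |
| C, one-month in-person margin at each closure edge | 8.8-12.8%; 6.0-10.9% |
| C, delayed Year 3 timing | 9.8-13.5%; 7.2-12.3% |

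With arm included the bias is below 0.1% in every setting. Adding an MMSE-type auxiliary and an MCI/dementia indicator to A and C moved results by 0.6 points or less. Repeating the calculation with uniform enrolment, a March start and a wider range of residual SDs gave 3.2-5.5% for A and 9.8-13.2% for C. If final attrition were 10% (assumed), A becomes 4.8-7.8% and C 9.3-16.9%.

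**6. Practical size.** At 0.028/year, 5.5% is 0.0015 and 14.1% is 0.0039 per year. One SE with complete data is about 0.09 × √(4/977) = 0.0058. For C at N = 977, null rejection is 0.026-0.036 without arm and 0.051-0.065 with it. Power for 0.023/year is 0.93-0.97 without arm and 0.95-0.98 with it.

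**The case against.** The best reply is that arm was taken for granted. The list says what the model will include, not that nothing else enters, and no sentence says that imputation is pooled. SAP 7.4(d) offers control-based imputation of the hearing-aid arm as a departure from the primary analysis, a contrast that makes most sense if the primary imputation respects arm. SAP 7.4(c) treats the imputation model as the analysis variables plus auxiliaries, and arm is an analysis variable. The inputs were tuned at version 4.0 while treatment assignments were to stay blinded until database lock, so arm could not have been assessed then. That last step is inference, but it explains the gap without any decision to exclude arm.

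This stands as evidence of intent, and a reader should not infer that arm was deliberately left out. It does not put arm in the specification: an analyst who follows either list omits it.

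The second reply is that the effect is small and conservative and that full-information maximum likelihood would expose it. The first half stands. The second stands in part: that analysis conditions on arm, but the SAP 7.4 analyses are optional and this one's stated purpose is different.

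A caution on the power comparison: with arm included, null rejection reached 0.065. The Monte Carlo SE at 2000 trials is √(0.05 × 0.95/2000) = 0.005, so the two powers are not compared at exactly equal size.

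**Conclusion.** The omission is in the text of both documents. The direction of the bias follows from it whenever the true effect is not zero; under no effect there is none. The size is conditional: roughly 0.6-5% from the reported attrition (ceiling about 7%), about 4-6% if only Year 3 scores are imputed, and about 5.5-14% if closure-missed Year 1 and 2 scores are imputed as well. Enrolment shape, dropout timing, share of deaths and residual SD are all assumed.

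A reader might infer that the primary estimate will be understated by 7-14%, or by more at the design attrition of 27.1%. The documents do not support either as a headline. Reported attrition was 6.7% and includes deaths, whose later scores are outside the primary focus. SAP 7.1 can be read as imputing only the final visit. The reference in item (5) of SAP 7.3 to missed visits supports imputing earlier ones but does not say so outright. Nor is the validity of the test threatened: false positives are not inflated, the shift is below one SE, and the power cost is about 1-2 points. The point is worth fixing because it is an avoidable understatement of the effect size.

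**What to change.** In SAP 7.3 and Protocol 12.2, state that randomised arm and its interaction with visit or time are in the imputation model, or that imputation is run separately within arm, in either case after database lock. Apply the same rule to the memory, executive function and language scores. If arm was always intended, that sentence is all that is needed.

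The cost is one sentence per document and one term, or a by-arm statement, in the imputation code. The few extra parameters are negligible at about 490 participants per arm.
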